2.8.4 Other safety data

2.8.4.1 ECG

A standard 12-lead electrocardiogram (ECG) will be performed at Screening (source data) and will be reviewed locally. ECG data will not be analyzed.

2.8.4.2 Vital signs

Notable vital signs abnormalities will be analyzed by treatment group for the DBTP and the entire study period. A frequency table will be provided.

Normal blood pressure will be defined as systolic blood pressure (SBP) of 90 to < 120 mmHg, and diastolic blood pressure of 60 to < 80 mmHg under the measurement conditions outlined in the protocol. Notable blood pressure findings will be hypertension (SBP of ≥ 140 mmHg and/or diastolic blood pressure [DBP] of ≥ 90 mmHg) or hypotension (SBP of < 90 mmHg and/or a DBP of < 60 mmHg).

A normal pulse rate will be defined as a rate of 60 to 100 beats per minute (bpm). Notable pulse rate abnormality will be a rate below 60 bpm (bradycardia) or above 100 bpm (tachycardia).

2.8.4.3 Pregnancy

Serum pregnancy test results will be listed for women of childbearing potential.

2.9 Pharmacokinetic endpoints

Not applicable.

2.10 PD and PK/PD analyses

Not applicable.

2.11 Patient-reported outcomes

The only patient reported outcome (PRO) assessed in the study is the GO-QoL. Summary statistics will be provided by treatment and visit.

2.12 Biomarkers

Not applicable,

2.13 Other Exploratory analyses

Not applicable.

2.14 Interim analysis

Due to premature study discontinuation, no interim analysis is planned.

3 Sample size calculation

A final number of 28 patients is expected to be randomized by the time of study discontinuation. Therefore, all analyses will be performed and interpreted in a purely descriptive manner.

4 Change to protocol specified analyses

Due to premature study discontinuation, purely descriptive analyses will be performed for primary and secondary endpoints. Exploratory endpoints will not be analyzed.

5 Appendix

5.1 Imputation rules

5.1.1 Concomitant medication date imputation

Incomplete day

Incomplete start day will be imputed as MAX(date of study day 1, *earliest possible start date*).

Incomplete end day will be imputed as MIN(EoS, *latest possible end date*).

Earliest possible start/end date is calculated on the eCRF page and refers to the first day of the corresponding month. *Latest possible start/end date* is calculated on the eCRF page and refers to the last day of the corresponding month.

Incomplete day/month

Incomplete start day/month will be imputed as MAX(date of study day 1, 01-Jan of the year entered).

Incomplete end day/month will be imputed as MIN(EoS, 31-Dec of the year entered).

Incomplete day/month/year

Incomplete day/months/year will not be imputed.

If the imputed end date is less than the existing start date, use the start date as the imputed end date.

5.1.2 Prior medications/ therapies date imputation

Prior medications/ therapies are those with an end date prior to the treatment phase (first drug administration).

Incomplete day

Incomplete start day will be imputed as earliest possible start date.

Incomplete end day will be imputed as MIN (date of the day prior to study day 1, latest possible end date).

Incomplete day/month

Incomplete start day/month will be imputed as 01-Jan of the year entered.

Incomplete end day/month will be imputed as MIN(31-Dec of the year entered, date of the day prior to study day 1).

Incomplete day/month/year

Incomplete start date will be imputed as very early date, e.g., 01JAN1900.

Incomplete end date will be imputed as a date of the day prior to study Day 1.

For “Date of onset of TED symptoms” and “date of first diagnosis of TED”, the date will be imputed in the same way as prior medication/ therapies start date.

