### 5.1 Inclusion criteria

Patients eligible for inclusion in this study must meet all of the following criteria:

- 1. Patient must be able to understand and communicate with the investigator and comply with the requirements of the study and must give a written, signed and dated informed consent before any study assessment is performed.
- 2. Male or non-pregnant, non-lactating female patients  $\geq 18$  years of age.
- 3. Clinical diagnosis of active, moderate to severe TED (not sight-threatening) in the study eye at Baseline associated with two or more of the following:
  - Lid retraction  $\geq 2$  mm.
  - Moderate or severe soft tissue involvement.
  - Exophthalmos  $\geq$  3 mm above normal
  - Inconstant or constant diplopia.
- 4. Onset of TED symptoms fewer than 12 months prior to Baseline.
- 5. Clinical activity score  $(CAS) \ge 4$  (on a 7-point scale, with a score of  $\ge 3$  indicating active TED) in the more severely affected (study) eye at Screening and Baseline. (Proptosis is the primary qualifier for selection of the study eye. In case both eyes show a similar degree of proptosis, other inflammatory signs and symptoms (CAS) should be taken into account by the investigator for the selection of the study eye).
- 6. Peripheral euthyroidism or mild hypo-/hyperthyroidism defined as fT3 and fT4 < 30% above/below normal limits at Screening. Every effort should be made to correct the mild hypo-/hyperthyroidism promptly and to strictly maintain the euthyroid state until the end of this study.

Note: Central lab retests will be allowed during the Screening Period (day -42 to -1) if fT3 and fT4 values are outside the above-mentioned cut-off criteria.

7. Orbital MRI assessment available confirming the diagnosis of TED for patients initially presenting with hypo- or euthyroidism (without treatment for hyperthyroidism) before or at the time of TED diagnosis (to rule-out other potential causes of the orbital signs and symptoms).

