2.3.4 TED and thyroid medical history

Disease history collected at Screening contains information on the TED and thyroid medical history. Descriptive analyses will be done for time since onset of TED symptoms, time since first diagnosis of TED and underlying thyroid condition based on the FAS.

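### The SAP imputes incomplete TED onset and diagnosis dates with the medication start-date rule, although these dates are then used to calculate and summarise disease duration

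*SAP*

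**What the plan says.** SAP 5.1.2 is written for prior medications and therapies. Its start-date rules have three levels:

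- Day missing: "Incomplete start day will be imputed as earliest possible start date". SAP 5.1.1 explains that the earliest possible date "refers to the first day of the corresponding month".
- Day and month missing: "Incomplete start day/month will be imputed as 01-Jan of the year entered".
- Whole date missing: "Incomplete start date will be imputed as very early date, e.g., 01JAN1900".

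The section closes by extending these rules to the onset and first-diagnosis dates of TED: "the date will be imputed in the same way as prior medication/ therapies start date".

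SAP 2.1.1.3 defines two durations in years, Baseline visit date minus onset date and Baseline visit date minus diagnosis date. SAP 2.3.4 reports them on the FAS: "Descriptive analyses will be done for time since onset of TED symptoms", and likewise for diagnosis. SAP 2.1 and 2.3.2 give continuous data as N, mean, SD, median, minimum and maximum. Nothing caps or excludes imputed dates, and SAP 5.1.4 (Other imputations) is marked not applicable.

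Protocol 5.1, inclusion criterion 4, requires "Onset of TED symptoms fewer than 12 months prior to Baseline".

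**The concern.** An early placeholder does no harm for a prior medication. SAP 2.4.2 tabulates medications by ATC class and preferred name, and no duration is calculated from the start date. For TED history the date is the measurement, so the placeholder becomes data. Every level of the rule picks the earliest possible date. Errors therefore only lengthen the duration and cannot average out.

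The rule also ignores what the protocol says about onset in an eligible patient, namely that it lies less than 12 months before Baseline. With 28 patients randomized, one record can distort the mean, SD and maximum of time since onset or time since diagnosis.

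The treatment of fully missing dates is also out of step with the rest of the SAP. SAP 5.1.1 does not impute a fully missing concomitant-medication date, SAP 2.5.3 and 2.6.3 do not replace missing endpoint values, and SAP 2.8 does not impute missing safety data.

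**Working it through.** The plan gives no figure on this point, so there is none to reproduce. The check applies the three rules by date arithmetic.

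**Inputs.** From the documents: the imputation rules (SAP 5.1.2, 5.1.1), the duration definition (SAP 2.1.1.3), the onset criterion (Protocol 5.1), 28 randomized (SAP section 3) and 1:1 allocation (Protocol section 3). Assumed: Baseline dates spread evenly over 2021 or 2022, onset uniform over the eligible window, 14 patients per arm, and a mean of 0.5 years in patients with complete dates. An imputed onset 12 months or more before Baseline counts as failing the criterion.

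**Whole date missing.** For Baseline 15 Jun 2022, the time from 1 Jan 1900 is 122.45 years. Over all Baselines in 2021 and 2022 the range is 121 to 123 years, so an onset date imputed this way always fails the criterion. One such record gives:

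- Arm of 14: mean = (13 × 0.5 + 122.45)/14 = 9.2 years, a rise of (122.45 − 0.5)/14 = 8.7 years.
- All 28: mean = (27 × 0.5 + 122.45)/28 = 4.9 years.

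**Day and month missing (onset).** Take Baseline on day d of a 365-day year. There are 364 eligible onset days, of which 365 − d fall in the previous calendar year. Those are imputed to 1 January of that year, which is 12 months or more before Baseline. Onsets in the Baseline year are imputed to 1 January of the same year and never fail. Averaged over d = 1 to 365, the share failing is (365 − 183)/364 = 182/364 = 50%. Enumerating every eligible pair of dates also gives 50% for each Baseline year. The mean duration goes from 0.50 to 1.00 years, and the longest is just under 2 years.

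Example with Baseline 15 Jun 2022:

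| Recorded onset | True onset | Imputed onset | True duration | Imputed duration |
|---|---|---|---|---|
| 2021 | 20 Oct 2021 | 1 Jan 2021 | 7.8 months | 17.4 months |
| 2022 | any day in 2022 before Baseline | 1 Jan 2022 | 5.4 months or less | 5.4 months |

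**Day missing only (onset).** The criterion fails only if onset lies in the same calendar month as Baseline minus 12 months, and after that day. On average this covers (7 × 465 + 4 × 435 + 378)/365 = 14.7 days, and 14.7/364 = 4%. Enumeration gives the same. The shift is at most 30 days and the longest duration is 1.08 years.

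**Check of a bounded midpoint.** For onset recorded as 2021 and Baseline 15 Jun 2022, the possible eligible dates run from 16 Jun to 31 Dec 2021. The midpoint is 23 Sep 2021, which is 265 days or 8.7 months. That is 0.9 months from the true 7.8, against 9.6 months under the current rule.

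**The case against.** The strongest reply is that the damaging case is unlikely and its consequences small.

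**Likelihood.** Onset timing is an entry criterion, and its date is a named eCRF item (Protocol 8.2.5). Sites confirm all criteria before randomization (6.3.2), missing values are queried (11.2), and monitors verify adherence to the inclusion and exclusion criteria in full (11.3). A patient with no onset year should not have been randomized. This stands for onset. It protects the diagnosis date less, because no criterion depends on that date.

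**Consequence.** The SAP also reports the median, which one extreme value barely moves. Duration is not a stratum, a covariate in the protocol's primary model or a subgroup. After early termination, superiority testing is omitted. All of this stands and limits the point to a descriptive table.

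**Stronger readings.** A reader might infer that the rule makes eligible patients count as ineligible. The documents do not support this. No SAP text derives eligibility from the imputed duration, and deviations are reported separately (SAP 2.3.1). A reader might also infer that every incomplete date breaches the criterion, or that diagnosis durations do. Neither follows. Year-only onset dates fail in about half of eligible pairs and day-only dates in about 4%, and the protocol sets no limit on time since diagnosis.

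**Remedy.** A plain midpoint has faults of its own. With onset recorded as 2022, diagnosis on 1 Feb 2022 and Baseline on 15 Jun 2022, it places onset in late March, after diagnosis. A lower bound at 12 months leaves no valid date when the recorded period lies wholly earlier, and it could hide a real eligibility deviation. These objections are sound, and the fix has to meet them. That the current rule is simple and stated in advance does not justify entering 1900 into a mean.

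**Conclusion.** The point holds as a minor one. Followed as written, SAP 5.1.2 puts a false value of about 122 years into the disease-history table for any fully missing onset or diagnosis date. It can also report up to about 2 years since onset for an eligible patient whose onset is known only by year. Day-only gaps can be ignored in practice.

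The 8.7-year rise in an arm mean assumes 14 patients per arm, a mean of 0.5 years in the others, Baseline in mid-2022 and use of 01JAN1900, which the SAP gives only as an example. The one-half share assumes uniform dates. The documents do not say how many dates are incomplete, so the actual effect may be nil. No eligibility decision, endpoint or test depends on these durations.

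**What to change.** Replace the last sentence of SAP 5.1.2 with a separate rule for the two TED dates:

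- **Fully missing onset or diagnosis date:** leave missing and report the count.
- **Partial onset date:** impute within the recorded month or year, after Baseline minus 12 months and no later than the earlier of the diagnosis date and Baseline, for example at the midpoint. If no date meets these bounds, keep the date within the recorded period and flag the record as a possible eligibility deviation.
- **Partial diagnosis date:** impute within the recorded period, not before a known onset date and not after Baseline.
- **All imputed values:** flag them, so that an imputed duration under 12 months is not read as evidence that the criterion was met.

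Keep the current rule for medications and therapies. The cost is a few sentences in the SAP and a small change to one derivation. If every date turns out to be complete, no output changes.

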5.1.3 Post therapies date imputation

Not applicable.

5.1.4 Other imputations

Not applicable.

5.2 AEs coding/grading

Adverse events are coded using the Medical Dictionary for Regulatory Activities (MedDRA) terminology.

Severity of adverse events is graded by investigator (mild, moderate, severe) and documented in the eCRF.

5.3 Laboratory parameters derivations

Not applicable.

5.4 Statistical models

5.4.1 Primary analysis

Not applicable.

5.4.2 Key secondary analysis

Not applicable.

5.4.3 Safety analysis

Crude incidence and $100*(1-\alpha)\%$ confidence interval

For n subjects, each at risk to experience a certain event with probability π , the crude incidence is estimated as $p=x/n$, where x is the number of subjects with the event.

Absolute and relative frequencies will be displayed as well as 95% CI for the relative frequency based on the score method including continuity correction ([Newcombe 1998](#)).

With z as $(1-\alpha/2)$ -quantile of the standard normal distribution (SAS: $z=PROBIT(1-\alpha/2)$), n as total number of subjects (i.e., number of subjects in the denominator), and p as estimated crude incidence (number of subjects with event / n) it is $q=1-p$.

Then the lower limit is:

$$L = \max(0, \frac{2np + z^2 - 1 - z\sqrt{z^2 - 2 - 1/n + 4p(nq + 1)}}{2(n + z^2)})$$

And the upper limit is:

$$U = \min \left(1, \frac{2np + z^2 + 1 + z \sqrt{z^2 + 2 - 1/n + 4p(nq + 1)}}{2(n + z^2)} \right)$$

Note: if $p < L$ then $L = p$ and if $p > U$ then $U = p$.

Exposure adjusted incidence rate and 100*(1- α)% confidence interval

It will be assumed that for each of n subjects in a clinical trial the time t_j ($j=1, \dots, n$) to the first occurrence of a certain treatment emergent event is observed, or if the event was not experienced, the (censored) time to the end of the observation period or last dose plus 84 days whichever occur earlier. The sequence of first occurrence of an event will be modelled to follow approximately a Poisson process with constant intensity Θ . The parameter Θ will be estimated as $\lambda = D/T$, where T is the sum of t_1 to t_n and D is the number of subjects with at least one event.

Conditionally on T , an exact 100* $(1-\alpha)\%$ CI for a Poisson variable with parameter ΘT and observed value D can be obtained based on [Garwood 1936](#) from which an exact 100* $(1-\alpha)\%$ CI for D/T will be derived as follows ([Sahai 1993](#); [Ulm 1990](#)):

Lower confidence limit $L = \frac{0.5c_{\alpha/2,2D}}{T}$ for $D > 0$, 0 otherwise,

Upper confidence limit $U = \frac{0.5c_{1-\alpha/2,2D+2}}{T}$

where $c_{\alpha k}$ is the α th quantile of the Chi-square distribution with k degrees of freedom.

Table 5-1 Examples for calculating exposure time for incidence rates (IR)

1st treatment / total exposure time	2nd treatment / total exposure time	AE event onset (in days from study start)	Exposure for IR
Placebo / 100 days	AIN457 / 200 days	Day 50 (during 1st treatment)	Placebo: 50 days
		Day 110 (10 days into 2nd treatment)	AIN457: 10 days Any AIN: 10 days

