SOC	System Organ Class
TEAE(s)	Treatment-Emergent Adverse Event(s)
TED	Thyroid Eye Disease
TFLs	Tables, Figures, Listings

1 Introduction

The purpose of this statistical analysis plan (SAP) is to provide details of the statistical analysis according to Section 12 of the study protocol v02 for AIN457 (secukinumab) Study CAIN457ADE16 dated 15-Mar-2022. The scope of this plan includes the primary and secondary analyses. The purpose of this amendment is to modify the analysis plan to reflect the early termination status of the study. At the time of termination, 28 patients had been randomized, 25 patients had completed the double-blind treatment period, and 23 patients had entered the follow-up period.

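### SAP 5.4.3: the upper 95% limit for crude adverse-event incidence has nq + 1 under the root where nq − 1 is needed, so upper limits are too high by up to 4.5 percentage points at 14 patients per arm

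*SAP*

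**What the plan says.** SAP Section 5.4.3 (Safety analysis) defines the crude incidence: "the crude incidence is estimated as $p=x/n$, where x is the number of subjects with the event". It sets q = 1 − p, takes z as the (1 − α/2) "quantile of the standard normal distribution", and names the interval: "Absolute and relative frequencies will be displayed as well as 95% CI for the relative frequency based on the score method including continuity correction". Two explicit formulas follow.

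- Introduced by "Then the lower limit is": `L = max(0, [2np + z² − 1 − z·sqrt(z² − 2 − 1/n + 4p(nq + 1))] / [2(n + z²)])`
- Introduced by "And the upper limit is": `U = min(1, [2np + z² + 1 + z·sqrt(z² + 2 − 1/n + 4p(nq + 1))] / [2(n + z²)])`

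A boundary note then resets L to p when p is below L, and U to p when p is above U. SAP Section 2.8.1 refers to Section 5.4.3 for the crude incidences in the adverse-event overview table. On numbers, SAP Section 1 says: "At the time of termination, 28 patients had been randomized".

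**The concern.** Going from the lower to the upper limit of this interval, every sign that comes from the continuity correction should reverse. Three do: −1 becomes +1, −2 becomes +2, and −z becomes +z. The +1 inside 4p(nq + 1) does not. If that is an error, the printed upper limit is not the limit of the method the SAP names, and it does not match the SAP's own lower limit.

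At stake are the upper confidence limits for crude adverse-event incidence. The trial stopped early, superiority testing was dropped and efficacy is reported descriptively, so the safety summaries are a main remaining output. A program that follows the formula literally gives wrong upper limits. A program that uses a standard routine for the named method gives output that disagrees with the SAP.

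**Working it through.** **Inputs.** p = x/n, q = 1 − p, α = 0.05 two-sided, z = 1.95996, z² = 3.84146 (SAP 5.4.3). Arm size n = 14 is an assumption: 28 randomised (SAP 1), allocated 1:1 (SAP 1.1). The SAP gives no worked numerical example, so there is no stated figure to reproduce first.

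**1. Derivation from the method.** The upper limit θ solves θ − p − 1/(2n) = z·sqrt(θ(1 − θ)/n).

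- Put c = p + 1/(2n), square, and multiply by n: (n + z²)θ² − (2np + 1 + z²)θ + nc² = 0, where nc² = np² + p + 1/(4n).
- The discriminant is (2np + 1 + z²)² − 4(n + z²)(np² + p + 1/(4n)).
- The terms without z cancel, leaving z²[z² + 2 − 1/n + 4np − 4np² − 4p] = z²[z² + 2 − 1/n + 4p(nq − 1)].

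The upper limit therefore needs nq − 1. The same steps with c = p − 1/(2n) give z² − 2 − 1/n + 4p(nq + 1), which is the printed lower limit. The lower limit is correct.

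**2. Check from the SAP alone.** Counting non-events instead of events swaps p and q, so U(x) must equal 1 − L(n − x). With p and q swapped, the radicand of the printed lower limit becomes:

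z² − 2 − 1/n + 4q(np + 1) = z² − 2 − 1/n + 4npq + 4(1 − p) = z² + 2 − 1/n + 4p(nq − 1).

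The printed upper radicand is larger than this by 4p × 2 = 8p. The excess is therefore nil at p = 0, and under the root it grows with p.

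**3. Numbers at n = 14.** The denominator is 2(14 + 3.84146) = 35.683.

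7/14 (p = 0.5, nq = 7):
- Printed U: (14 + 4.84146 + 1.95996·sqrt(5.77003 + 16)) / 35.683 = (18.84146 + 9.1449) / 35.683 = 78.4%
- With nq − 1: (18.84146 + 1.95996·sqrt(5.77003 + 12)) / 35.683 = (18.84146 + 8.2621) / 35.683 = 76.0%
- Printed L: (16.84146 − 8.2621) / 35.683 = 24.0%, whose mirror image is 76.0%. The printed pair, 24.0% to 78.4%, is not symmetric about 50%.

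11/14 (4p = 3.14286, nq = 3):
- Printed U: (26.84146 + 1.95996·sqrt(5.77003 + 12.57143)) / 35.683 = 98.75%
- With nq − 1: (26.84146 + 1.95996·sqrt(5.77003 + 6.28571)) / 35.683 = 94.29%

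| x/14 | Printed U | U with nq − 1 | Excess (points) |
|---|---|---|---|
| 0 | 26.8% | 26.8% | 0 |
| 1 | 36.3% | 35.8% | 0.5 |
| 4 | 59.5% | 58.0% | 1.5 |
| 7 | 78.4% | 76.0% | 2.5 |
| 9 | 89.3% | 86.0% | 3.3 |
| 10 | 94.2% | 90.4% | 3.8 |
| 11 | 98.75% | 94.3% | 4.45 |
| 12 | 100% (capped; 102.8% before) | 97.5% | 2.5 |
| 13 | 100% (capped; 106.4% before) | 99.6% | 0.4 |
| 14 | 100% | 100% (after the note) | 0 |

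**4. Numerical confirmation.** Solving the score equation numerically at n = 14 and n = 28 reproduces the nq − 1 form for every x < n and the printed lower limit for every x ≥ 1. The printed upper limit exceeds the solution for every 0 < x < n. For x < n a true solution must lie below 1, so the uncapped 102.8% at 12/14 cannot be one.

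**5. Dependence on arm size.** The largest excess is 4.86 points at n = 12, 4.65 at 13, 4.45 at 14, 4.27 at 15, 4.10 at 16 and 2.72 at 28.

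**The case against.** The strongest objection is provenance. The finding is one sign in a typeset formula that a program read from PDF, and a minus misread as a plus would produce exactly this text. The algebra shows that the formula as read is wrong. It cannot show that the SAP page is wrong. This stands as a caveat: the sign has to be confirmed on the original page.

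The second objection is consequence, and most of it stands. The error only widens the interval, which is the cautious direction for harms. For events in 1 to 4 of 14 patients it is 0.5 to 1.5 points, and the 4.45-point figure belongs to a single cell. SAP Section 3 makes all analyses descriptive, and no safety test or threshold uses these limits. Reach is also limited: only the overview-table sentence in Section 2.8.1 refers to Section 5.4.3, and the tables by system organ class, preferred term and severity are specified as counts and percentages without intervals.

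Third, the method is named correctly in words, so a programmer using a validated routine would get the right limit. That is true, but the output would then contradict the printed formula, which still has to be corrected.

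The boundary note is only supporting evidence. With nq − 1 the upper limit at 14/14 is 0.993, below p = 1, so the note has work to do. With nq + 1 it is 1.092 before capping, so the upper half of the note does nothing there. That half could, however, have been written simply to match the lower one, which is needed at x = 0 (raw L = 0.0066) in either case.

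**Conclusion.** The concern holds. As printed, the upper limit in SAP 5.4.3 is not the continuity-corrected score limit and is inconsistent with the SAP's own lower limit. It is too high for every 0 < x < n: by 0.4 to 4.45 points at an assumed 14 per arm, with a maximum of 4.1 to 4.9 points for arms of 16 down to 12, and 2.7 points for a group of 28. The excess peaks at 11/14 and then shrinks because of the cap at 100%.

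Point estimates, lower limits and exposure-adjusted rates are not affected, and no conclusion of the trial turns on the error. It is a clear formula error with a small practical effect and should be corrected as routine, not treated as critical. The conclusion rests on the formula having been read correctly from the PDF. The percentage-point figures also rest on the assumed arm size.

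**What to change.** In the upper-limit formula of SAP 5.4.3, replace 4p(nq + 1) with 4p(nq − 1). Leave the lower limit, the caps at 0 and 1, and the boundary note as they are.

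Confirm the sign on the original SAP page first, then check the safety program. Two quick tests are that 7/14 returns 24.0% to 76.0%, and that U(4/14) and L(10/14) sum to 100% (58.0% + 42.0%). If any tables were produced with the printed form, rerun the crude-incidence intervals.

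The cost is one sign in the SAP and, if the formula was hand-coded, one line of the program. No new data or additional analysis is needed.
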